5.4.5 Order of Assessments

The following sequence order will be in effect when more than one assessment is required at a time point with blood sampling for pharmacokinetics being collected nearest to the scheduled time point:

1. Vital signs
2. ECG
3. Laboratory assessments (hematology, chemistry and hepatic panel) blood draw
4. Pharmacokinetic blood draw

5.5 Adverse Events and Other Safety Aspects

5.5.1 Definition of Adverse Events

An AE is any untoward medical occurrence in a subject administered a study drug, and which does not necessarily have to have a causal relationship with this treatment. An AE can therefore be any unfavorable and unintended sign (including an abnormal laboratory finding), symptom or disease (new or exacerbated) temporally associated with the use of a medicinal product whether or not considered related to the medicinal product.

In order to identify any events that may be associated with study procedures and could lead to a change in the conduct of the study, Astellas collects AEs even if the subject has not received study drug treatment. AE collection begins after the signing of the ICF and will be collected until 60 days after the last dose of study drug or the subject is determined to be a screen failure.

Care will be taken not to introduce bias when detecting AEs and/or SAEs. Open-ended and non-leading verbal questioning of the subject is the preferred method to inquire about AE occurrences.

5.5.1.1 Abnormal Laboratory Findings

Any abnormal laboratory test result (e.g., hematology, clinical chemistry, hepatic panel or INR) or other safety assessment (e.g., ECGs, vital signs measurements, physical examination), including those that worsen from baseline, that is considered to be clinically significant in the medical and scientific judgment of the investigator and not related to underlying disease, is to be reported as an SAE or AE ((S)AE).

Any clinically significant abnormal laboratory finding or other abnormal safety assessment which is associated with the underlying disease does not require reporting as an (S)AE, unless judged by the investigator to be more severe than expected for the subject's condition.

Repeating an abnormal laboratory test or other safety assessment, in the absence of any of the above criteria, does not constitute an AE. Any abnormal test result that is determined to be an error does not require reporting as an AE.

5.5.1.2 Potential Cases of Drug-Induced Liver Injury

Refer to [Appendix 12.5 Liver Safety Monitoring and Assessment] for detailed instructions on drug induced liver injury. Abnormal values in AST and/or ALT concurrent or with abnormal elevations in TBL that meet the criteria outlined in [Appendix 12.5 Liver Safety Monitoring and Assessment], in the absence of other causes of liver injury, are considered potential cases of drug-induced liver injury (including potential Hy's Law cases) and are always to be considered important medical events and reported per [Section 5.5.5 Reporting of Serious Adverse Events].

5.5.1.3 Disease Progression and Study Endpoints

Under this protocol, the following event(s) will not be considered as an (S)AE:

- Pre-planned and elective hospitalizations or procedures for diagnostic, therapeutic or surgical procedures for a pre-existing condition that did not worsen during the course of the clinical trial. These procedures are collected per the eCRFs Completion Guidelines.

5.5.2 Definition of Serious Adverse Events (SAEs)

An AE is considered “serious” if, in the view of either the investigator or sponsor, it results in any of the following outcomes:

- Results in death
- Is life-threatening (an AE is considered “life-threatening” if, in the view of either the investigator or sponsor, its occurrence places the subject at immediate risk of death. It does not include an AE that, had it occurred in a more severe form, might have caused death)
- Results in persistent or significant disability/incapacity or substantial disruption of the ability to conduct normal life functions
- Results in congenital anomaly or birth defect
- Requires inpatient hospitalization (except for planned procedures as allowed per study) or leads to prolongation of hospitalization (except if prolongation of planned hospitalization is not caused by an AE). Hospitalization for treatment/observation/examination caused by AE is to be considered as serious.
- Other medically important events (defined in paragraph below)

Medical and scientific judgment should be exercised in deciding whether expedited reporting is appropriate in other situations, such as important medical events that may not be immediately life-threatening or result in death or hospitalization, but may jeopardize the subject or may require intervention to prevent one of the other outcomes listed in the definition above. These events, including those that may result in disability/incapacity, usually are considered serious. Examples of such events are intensive treatment in an emergency room or at home for allergic bronchospasm; blood dyscrasias or convulsions that do not result in hospitalization; or development of drug dependency or drug abuse.

5.5.2.1 Always Serious Adverse Events

The sponsor has a list of events that they classify as “always serious” events. If an AE is reported that is considered by the sponsor to be an SAE per this classification as “always serious”, additional information on the event (e.g., investigator confirmation of seriousness, causality) will be requested.

5.5.3 Criteria for Causal Relationship to Study Drug

A medically qualified investigator is obligated to assess the relationship between the study drug and each occurrence of each (S)AE. This medically qualified investigator will use medical judgment, as well as the Reference Safety Information (refer to the IB) to determine the relationship. The causality assessment is one of the criteria used when determining regulatory reporting requirements.

The medically qualified investigator is requested to provide an explanation for the causality assessment for each (S)AE and must document in the medical notes that he/she has reviewed the (S)AE and has provided an assessment of causality.

Following a review of the relevant data, the causal relationship between the study drug and each (S)AE will be assessed by answering ‘yes’ or ‘no’ to the question “**Do you consider that there is a reasonable possibility that the event may have been caused by the study drug**”.

When making an assessment of causality, the following factors are to be considered when deciding if there is evidence and/or arguments to suggest there is a ‘reasonable possibility’ that an (S)AE may have been caused by the study drug (rather than a relationship cannot be ruled out) or if there is evidence to reasonably deny a causal relationship:

- Plausible temporal relationship between exposure to the study drug and (S)AE onset and/or resolution. Has the subject actually received the study drug? Did the (S)AE occur in a reasonable temporal relationship to the administration of the study drug?
- Plausibility; i.e., could the event been caused by the study drug? Consider biologic and/or pharmacologic mechanism, half-life, literature evidence, drug class, preclinical and clinical study data, etc.
- Laboratory or other test results; a specific lab investigation supports the assessment of the relationship between the (S)AE and the study drug (e.g., based on values pre-, during and post-treatment)
- Available alternative explanations independent of study drug exposure; such as other concomitant drugs, past medical history, concurrent or underlying disease, risk factors including medical and family history, season, location, etc. and strength of the alternative explanation

There may be situations in which an SAE has occurred and the investigator has minimal information to include in the initial report to the sponsor. However, it is very important that the medically qualified investigator always make an assessment of causality for every event before the initial transmission of the SAE data to the sponsor. With limited or insufficient information about the event to make an informed medical judgment and in absence of any indication or evidence to establish a causal relationship, a causality assessment of ‘no’ is to be considered. In such instance, the investigator is expected to obtain additional information regarding the event as soon as possible and to re-evaluate the causality upon receipt of additional information. The medically qualified investigator may revise his/her assessment of causality in light of new information regarding the SAE and shall send an SAE follow-up report and update the eCRF with the new information and updated causality assessment.

5.5.4 Criteria for Defining the Severity of an Adverse Event

The investigator will use the following definitions to rate the severity of each AE:

- Mild: No disruption of normal daily activities
- Moderate: Affect normal daily activities
- Severe: Inability to perform daily activities

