5.4.2 Laboratory Assessments

Below is a table of the laboratory tests that will be performed during the conduct of the study and assessed by the local laboratory. In the event the protocol-specified clinical laboratory has already been collected and results available, these data are sufficient for monitoring safety as per the protocol and must be recorded in the eCRF. In order to minimize blood draws, it is not necessary to draw an additional sample for the sole purposes of the clinical trial.

Clinical laboratory samples should be collected at the same time as other blood samples such as pharmacokinetic whenever possible to minimize the need for unnecessary blood sampling for the subject. See [Table 1 and Table 2 Schedule of Assessment] for study visit days and allowed windows for lab sample collection.

Chemistry:	Hematology:
Sodium	Red blood cells
Potassium	White blood cells (total leukocytes)
Magnesium	Hemoglobin
Calcium	Hematocrit
Chloride	Platelets (thrombocytes)
Glucose	Neutrophils (ANC)
Creatinine	Eosinophils
Creatine phosphokinase/Creatine kinase	Basophils
Alkaline phosphatase (ALP)	Lymphocytes
	Monocytes
	Blast cells
Hepatic Panel:	Pregnancy Test:
Albumin	Human chorionic gonadotropin (hCG)
Total bilirubin (TBL)	
Direct Bilirubin	
Total Protein	Other:
Alanine aminotransferase (ALT)	Serum galactomannan (GM)
Aspartate aminotransferase (AST)	Partial thromboplastin time/international normalized ratio (PTT/INR)

Clinically significant out-of-range laboratory findings are to be determined and documented by the investigator/subinvestigator who is a qualified physician. Clinically significant changes will be recorded as AEs. At all scheduled time points during the clinical study, should any of the clinical laboratory test results be outside the normal range, the investigator may decide to repeat tests on new samples. A urine or serum pregnancy test will be performed for female subjects of childbearing potential prior to dosing, day 28, day 42 and day 84 (IA) or EOT, day 180 (IM) or EOT.

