12.5 Liver Safety Monitoring and Assessment

Any subject enrolled in a clinical study with active drug therapy and reveals an increase of serum aminotransferases (AT) to $> 3 \times \text{ULN}$ or bilirubin $> 2 \times \text{ULN}$ should undergo detailed testing for liver enzymes (including at least ALT, AST, alkaline phosphatase [ALP] and TBL). Testing should be repeated within 72 hours of notification of the test results. For studies for which a central laboratory is used, alerts will be generated by the central laboratory regarding moderate and severe liver abnormality to inform the investigator and study team. Subjects should be asked if they have any symptoms suggestive of hepatobiliary dysfunction.

Definition of Liver Abnormalities

Confirmed abnormalities will be characterized as moderate and severe where ULN:

	ALT or AST		TBL
Moderate	$> 3 \times \text{ULN}$	or	$> 2 \times \text{ULN}$
Severe	$> 3 \times \text{ULN}$	and	$> 2 \times \text{ULN}$

In addition, the subject should be considered to have severe hepatic abnormalities for any of the following:

- ALT or AST $> 8 \times \text{ULN}$.
- ALT or AST $> 5 \times \text{ULN}$ for more than 2 weeks.
- ALT or AST $> 3 \times \text{ULN}$ and International Normalized Ratio (INR) > 1.5 (If INR testing is applicable/evaluated).
- ALT or AST $> 3 \times \text{ULN}$ with the appearance of fatigue, nausea, vomiting, right upper quadrant pain or tenderness, fever, rash and/or eosinophilia ($> 5\%$).

The investigator may determine that abnormal liver function results, other than as described above, may qualify as moderate or severe abnormalities and require additional monitoring and follow-up.

Follow-up Procedures

Confirmed moderate and severe abnormalities in hepatic functions should be thoroughly characterized by obtaining appropriate expert consultations, detailed pertinent history, physical examination and laboratory tests. The site staff is to complete the liver abnormality case report form (LA-CRF). Subjects with confirmed abnormal liver function tests (LFTs) should be followed as described below.

Confirmed moderately abnormal LFTs should be repeated 2 to 3 times weekly then weekly or less if abnormalities stabilize or the study drug has been discontinued and the subject is asymptomatic.

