Severe hepatic liver function abnormalities as defined above, in the absence of another etiology, may be considered an important medical event and may be reported as a SAE. The sponsor should be contacted and informed of all subjects for whom severe hepatic liver function abnormalities possibly attributable to study drug are observed.

To further assess abnormal hepatic laboratory findings, the investigator is expected to:

- Obtain a more detailed history of symptoms and prior or concurrent diseases. Symptoms and new-onset diseases is to be recorded as “AEs” within the eCRF. Illnesses and conditions such as hypotensive events, and decompensated cardiac disease that may lead to secondary liver abnormalities should be noted. Nonalcoholic steatohepatitis is seen in obese hyperlipoproteinemic and/or diabetic subjects, and may be associated with fluctuating AT levels. The investigator should ensure that the medical history form captures any illness that predates study enrollment that may be relevant in assessing hepatic function.
- Obtain a history of concomitant drug use (including nonprescription medication, complementary and alternative medications), alcohol use, recreational drug use and special diets. Medications, is to be entered in the eCRF. Information on alcohol, other substance use and diet should be entered on the LA-CRF or an appropriate document.
- Obtain a history of exposure to environmental chemical agents.
- Based on the subject’s history, other testing may be appropriate including:
 - Acute viral hepatitis (A, B, C, D, E or other infectious agents),
 - Ultrasound or other imaging to assess biliary tract disease,
 - Other laboratory tests including INR, direct bilirubin.
- Consider gastroenterology or hepatology consultations.
- Submit results for any additional testing and possible etiology on the LA-CRF or an appropriate document.

Study Treatment Discontinuation

In the absence of an explanation for increased LFT’s, such as viral hepatitis, preexisting or acute liver disease or exposure to other agents associated with liver injury, the subject may be discontinued from study treatment. The investigator may determine that it is not in the subject’s best interest to continue study treatment. Discontinuation of study treatment should be considered if:

- ALT or AST $> 8 \times$ ULN.
- ALT or AST $> 5 \times$ ULN for more than 2 weeks.

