6.5.1 Adverse Events

TEAE is defined as an AE observed after starting administration of the study drug through 30 days after EOT. The number and percentage of subjects with treatment-emergent AEs, serious adverse events (SAEs), AEs leading to withdrawal of treatment, and AEs related to study drug will be summarized by MedDRA system organ class, MedDRA High Level term, and MedDRA preferred term for overall subjects and by subjects in each age cohort. The number and percentage of AEs by severity will also be summarized. All AEs will be listed.

A study drug-related TEAE is defined as any TEAE with a causal relationship of YES by the investigator. The incidence of treatment emergent AEs will be summarized by relationship to study drug and severity for all subjects and by each age cohort. The protocol defines how Treatment Emergent AEs are determined. Although all AEs are collected, the summary Table will be based on the TEAEs.

Clinically significant out-of-range laboratory findings are to be determined and documented by the investigator/subinvestigator who is a qualified physician. Clinically significant changes will be recorded as AEs.

An overview table will include the following:

- Number of TEAEs,
- Number and percentage of subjects with TEAEs,
- Number of drug related TEAEs,
- Number and percentage of subjects with drug related TEAEs,
- Number of serious TEAEs,
- Number and percentage of subjects with serious TEAEs,
- Number of serious drug related TEAEs,
- Number and percentage of subjects with serious drug related TEAEs,
- Number of TEAEs leading to permanent discontinuation of study drug,
- Number and percentage of subjects with TEAEs leading to permanent discontinuation of study drug, and
- Number of deaths.

The number and percentage of subjects with TEAEs, as classified by SOC, High Level Term (HLT), and PT will be summarized. Summaries will be provided for the following:

- TEAEs

- drug related TEAEs,
- serious TEAEs,
- drug related serious TEAEs,
- TEAEs leading to permanent discontinuation of study drug,
- drug related TEAEs leading to permanent discontinuation of study drug,

The number and percentage of subjects with TEAEs, as classified by SOC and PT will be summarized by time interval. For each adverse event in a particular interval, a subject will be counted if there is an onset of a treatment-emergent adverse event regardless of onset in other intervals.

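### Adverse-event severity is graded only by effect on daily activities, so an asymptomatic laboratory event is mild whatever its size and the severity tables understate such events

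*Protocol*

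**What the plan says.** **The scale.** Protocol 5.5.4 states: "The investigator will use the following definitions to rate the severity of each AE". The bottom level is "Mild: No disruption of normal daily activities" and the top level is "Severe: Inability to perform daily activities", with moderate between them. There is no exception for laboratory findings, and neither document contains a numeric toxicity scale.

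**How laboratory findings become adverse events.** Protocol 5.4.2 says: "Clinically significant changes will be recorded as AEs". Section 5.5.1.1 limits this to a result "that is considered to be clinically significant in the medical and scientific judgment of the investigator and not related to underlying disease". A disease-related finding is reportable only if the investigator judges it more severe than expected for that child.

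**The liver classes.** Appendix 12.5 sorts confirmed liver abnormalities into moderate and severe. Severe means ALT or AST above 3×ULN together with total bilirubin (TBL) above 2×ULN. It then extends the class: "In addition, the subject should be considered to have severe hepatic abnormalities for any of the following". A severe abnormality, "in the absence of another etiology, may be considered an important medical event and may be reported as a SAE". Section 5.5.1.2 treats potential drug-induced liver injury as an important medical event in every case and sends it through serious-event reporting.

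**The outputs.** SAP 6.5.1 says: "The number and percentage of AEs by severity will also be summarized". It also plans TEAEs by relationship and severity, overall and by age cohort. SAP 6.5.3 tabulates each child's highest liver values by ULN multiple and adds an eDISH plot. SAP 6.5.2 gives visit summaries, changes from baseline and low/normal/high shifts for laboratory tests.

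**The concern.** A biochemical abnormality that the child does not feel interferes with no activity. Under the literal definition it takes the lowest grade, however large it is. The error runs one way: mild is the bottom of the scale, so such an event can be under-graded relative to its size but never over-graded.

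This matters because the important risks here are partly measured rather than felt. Protocol 1.4 singles out liver toxicity for close monitoring. Protocol 1.2 reports that, in the earlier study of 27 children, the two withdrawals for adverse events were for raised liver enzymes and QT prolongation, both judged drug-related. A severity table with few or no severe laboratory events could reflect the scale rather than the drug.

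**Working it through.** The plan states no figure to reproduce. The check is a cross-reading of definitions.

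**Step 1: the chain.** A clinically significant laboratory change is recorded as an adverse event (5.4.2, 5.5.1.1). Each adverse event is rated by effect on activities (5.5.4). If there is no effect, the grade is mild. That grade goes into the severity tables (Protocol 7.5.1, SAP 6.5.1) with no re-grading rule.

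**Step 2: what Appendix 12.5 needs, and where SAP 6.5.3 shows it.**

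| Appendix 12.5 criterion | Laboratory values alone suffice? | Row in SAP 6.5.3 |
|---|---|---|
| Moderate: ALT or AST >3×ULN, or TBL >2×ULN | Yes | ALT >3× and TBL >2×; no AST-alone row |
| Severe: ALT or AST >3× with TBL >2× | Yes | Present |
| Severe: ALT or AST >8× | Yes | None |
| Severe: ALT or AST >5× for more than 2 weeks | Yes | ALT >5×, without duration; no AST-alone row |
| Severe: ALT or AST >3× with INR >1.5 | Yes | None |
| Severe: ALT or AST >3× with listed symptoms or eosinophilia >5% | Yes, through eosinophilia | None |

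Four of the five severe routes are purely laboratory, and the fifth can be met without symptoms. One of the five can be read directly from SAP 6.5.3.

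**Step 3: three asymptomatic values, each assumed to be recorded as an adverse event.** The rows are cumulative (>3×, >5×, >10×, >20×).

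| Peak ALT | Grade under 5.5.4 | Highest row reached in SAP 6.5.3 |
|---|---|---|
| 3.1×ULN | Mild | >3× |
| 9×ULN | Mild | >5× |
| 21×ULN | Mild | >20× |

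The severity table cannot tell these apart, but the liver table can. It cannot separate 9×ULN, which is severe in Appendix 12.5, from a brief isolated 6×ULN, which is moderate.

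**Step 4: baseline.** Exclusion criterion 2 removes children at ALT or AST of 5×ULN or more, or TBL of 3×ULN or more. A child may therefore enter with ALT between 3× and 5×ULN, which is moderate by value. With TBL also between 2× and 3×ULN, the values already meet a severe criterion. SAP 6.5.3 uses the highest value regardless of baseline, so baseline status must be shown for any such count to be interpretable.

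**Step 5: illustration.** Suppose k of 30 children have asymptomatic ALT above 8×ULN recorded as an adverse event, and there are no other severe hepatic events. The severity table shows 0/30 and a size-based table shows k/30. The gap is k/30: 0 for k = 0, 3.3 percentage points for k = 1, 6.7 for k = 2. For k = 2, with exact (Clopper-Pearson) 95% limits:

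- 0/30: upper limit 1 − 0.025^(1/30) = 11.6%, so 0 to 11.6%.
- 2/30 = 6.7%: limits from the 2.5% quantile of Beta(2, 29) and the 97.5% quantile of Beta(3, 28), so 0.8% to 22.1%.

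The documents give no expected rate, so k is an assumption. Only the direction follows from the text.

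**The case against.** The strongest reply is that the plan already reports liver safety by value. SAP 6.5.3 shows peak ALT at four ULN multiples, bilirubin, the combined criteria and an eDISH plot. Serious TEAEs and those leading to discontinuation are tabulated separately. Severity is also not prominent in SAP 6.5.1: none of the 11 items in the overview table, and none of the six summaries by system organ class, high level term and preferred term, is by severity. All of this stands. It confines the damage to the severity tables.

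Three stronger readings are tempting, and the documents do not support them.

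- A reader might infer that liver toxicity would be hidden. It would not, because of SAP 6.5.3 and the serious-event route.
- A reader might infer that Appendix 12.5 and Section 5.5.4 contradict each other. They do not set the same field. Appendix 12.5 classes a liver abnormality to direct work-up and follow-up; it does not assign an adverse-event grade. One word has two unlinked uses, so the report could show a serious hepatic event graded mild without explanation.
- A reader might infer a further bias because hospitalised children already have limited activities. The direction is unclear: existing limitation could push ratings up as easily as down.

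Replacing the investigator's grade with the Appendix 12.5 classes would also fail. There is no class below moderate, one severe route includes symptoms, and the classes refer to confirmed abnormalities.

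What the reply does not answer is the missing rows in Step 2. For other analytes, no planned table grades the size of an abnormality, and the visit summaries are not linked to adverse events.

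**Conclusion.** The point holds as a reporting defect of limited reach. Under the literal rule, asymptomatic laboratory events recorded as adverse events are always mild, and the TEAE-by-severity tables understate them. The planned liver table compensates only in part, and nothing comparable exists for other analytes.

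This rests on two assumptions: investigators apply Section 5.5.4 as written, and the finding passes the Section 5.5.1.1 test for being an adverse event. If some investigators grade by size instead, the table mixes two unstated standards, which is no better. The numerical size in this trial cannot be known in advance. The point concerns grading and tabulation only and bears on no treatment decision.

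**What to change.** Keep the investigator's severity grade and make three changes.

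1. **SAP 6.5.3.** Add the number and percentage of children meeting each laboratory-based moderate and severe criterion of Appendix 12.5, overall and by age cohort, with baseline status shown. This includes the AST-alone, >8×ULN, >5×ULN for more than 2 weeks, and INR rows. State how duration, confirmation and the pairing of ALT or AST with INR are derived. Name the source of the values: SAP 6.5.3 refers to a central laboratory, whereas Protocol 5.4.2 uses local ones.
2. **SAP 6.5.1.** In the severity tables, present TEAEs that are laboratory findings separately, with the peak value as a multiple of the normal limit. Alternatively, use one numeric toxicity scale, named in the SAP.
3. **Footnote to those tables.** State that the daily-activities grade does not reflect the size of a laboratory abnormality.

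The laboratory values are already recorded in the eCRF, so no new data collection is needed. The cost is one or two extra tables with their programming. The count of severe abnormalities may look less favourable than under the present plan.
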